6.5. Study Treatment Compliance

Not applicable.

6.6. Prior and Concomitant Medication

Prior medications concomitant medications will be coded using the WHO Drug Dictionary. The prior and concomitant medication will be listed for participants in the safety population by WHO drug class and WHO drug preferred term.

7. SAFETY AND TOLERABILITY

[Appendix A](#) provides a list of data displays.

7.1. General Considerations

The analyses for this section will be provided for the safety population. Summary tables may be replaced with listings when appropriate. For instance, an AE frequency table may be replaced with a listing if it only contains a few unique PTs reported on relatively few participants.

Unless otherwise stated, table summaries will be limited to TEAEs.

7.2. Adverse Events

7.2.1. Adverse Event Definitions

Adverse events that are ongoing at the time of rollover from the parent Protocol will be entered on the Adverse Event Form in the eCRF for this study.

A TEAE is any AE either reported for the first time in this Protocol and within 30 days of last dose of study treatment, or any AE ongoing and defined as treatment-emergent from the parent Protocol. Analysis of AEs (as discussed below) will be limited to TEAEs, but data listings will include all AEs regardless of their timing and in relation to study treatment administration. For purposes of analysis, all AEs will be considered TEAEs unless the AE can unequivocally be defined as not treatment-emergent.

Adverse events will be tabulated by MedDRA PT and SOC. Severity of AEs will be graded using the National Cancer Institute CTCAE v5.0. The CTCAE reporting guidelines and grading details are available on the Cancer Therapy Evaluation Program website.

A grading (severity) scale is provided for each AE term. If the toxicity is not included in the CTCAE v5.0 criteria, it will be rated on a scale of 1 to 5 as follows: 1 = mild, 2 = moderate, 3 = severe, 4 = life-threatening, and 5 = fatal. All toxicities will be graded based on the worst level reached, not the level they may have reached if they had not been treated. When the intensity of an AE changes over time for a reporting period (eg, between visits), each change in intensity will be reported as an AE until the event resolves.

The subset of AEs considered by the investigator to be related to study treatment will be considered to be treatment-related AEs. If the investigator does not specify the relationship of the AE to study drug, the AE will be considered to be treatment-related. The incidence of AEs and treatment-related AEs will be tabulated. Serious TEAEs will also be tabulated. In addition, serious TEAEs and serious AEs will be listed.

Any missing data pertaining to date of onset, causality, or severity must be queried for resolution. Unresolved missing causality and severity will be handled according to the following rules:

- An unresolved missing causality will be considered treatment-related.
- An unresolved missing severity will be identified as an unknown severity.

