8.3. Safety Assessments

8.3.1. Adverse Events

NOTE: Adverse events that are ongoing at the time of rollover from the parent protocol will be entered on the Adverse Event Form in the eCRF for this study.

Adverse events will be monitored from the time the participant signs the ICF until at least 30 days after the last dose of study treatment. Adverse events for enrolled participants that begin or worsen after informed consent should be recorded on the Adverse Event Form in the eCRF regardless of the assumption of a causal relationship with the study treatment. Adverse events

(including laboratory abnormalities that constitute AEs) should be described using a diagnosis whenever possible rather than by individual underlying signs and symptoms.

Adverse events will be reported by the participant (or, when appropriate, by a caregiver, surrogate, or the participant's legally authorized representative). The investigator and any qualified designees are responsible for detecting, documenting, and recording events that meet the definition of an AE or SAE and remain responsible for following up on AEs that are serious, considered related to the study treatment or procedures, or caused the participant to withdraw from the study. Care will be taken not to introduce bias when detecting AEs and/or SAEs. Open-ended and nonleading verbal questioning of the participant, such as "How are you feeling?", is the preferred method to inquire about AE occurrences. Adverse events may also be detected when they are volunteered by the participant between visits or through physical examinations, laboratory tests, or other assessments. The definition, reporting, and recording requirements for AEs are described in Section 9.

All SAEs will be reported to the sponsor or designee within 24 hours. The investigator will submit any updated SAE data to the sponsor within 24 hours of it being available.

After the initial AE/SAE report, the investigator is required to proactively follow each participant at subsequent visits/contacts. All SAEs will be followed until resolution, stabilization, the event is otherwise explained, or the participant is lost to follow-up (as defined in Section 7.3).

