8.6. Follow-Up

8.6.1. Safety Follow-Up

The safety follow-up period is the interval between the EOT visit and the scheduled follow-up visit, which should occur 30 to 35 days after the EOT visit. Adverse events and SAEs must be reported up until at least 30 days after the last dose of study treatment or until toxicities resolve, return to baseline, or are deemed irreversible, whichever is longer. Reasonable efforts should be made to have the participant return for the follow-up visit and report any AEs that may occur during this period.

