9.3. Recording and Follow-Up of Adverse Events and/or Serious Adverse Events

Adverse Event and Serious Adverse Event Recording

- Adverse events that are ongoing at the time of rollover to this study must be recorded on the Adverse Event Form in the eCRF for this study.
- An AE/SAE that begins or worsens after informed consent is signed should be recorded on the Adverse Event Form in the eCRF. AEs/SAEs should be reported for enrolled participants, but only SAEs need to be reported for screen failure participants. For detailed information, refer to the eCRF guidelines.
- When an AE/SAE occurs, it is the responsibility of the investigator to review all documentation (eg, hospital progress notes, laboratory reports, and diagnostic reports) related to the event.
- The investigator (or delegate) will then record all relevant AE/SAE information in the eCRF.
- It is **not** acceptable for the investigator to send photocopies of the participant's medical records in lieu of completing the Adverse Event Form in the eCRF.

- There may be rare instances when copies of medical records for certain cases are requested. In this case, all participant identifiers, with the exception of the participant number, will be redacted by the site staff on the copies of the medical records before submission. These records can be submitted to Incyte Pharmacovigilance by email/fax per the contact information listed as per SAE completing guidelines.
- The investigator will attempt to establish a diagnosis of the event based on signs, symptoms, and/or other clinical information. Whenever possible, the diagnosis (not the individual signs/symptoms) will be documented as the AE/SAE. When a clear diagnosis cannot be identified, each sign or symptom should be reported as a separate AE/SAE.

To the extent possible, each AE/SAE should be evaluated to determine the following:

- The severity grade (CTCAE v5.0 Grade 1 to 5). See below for further instructions on the assessment of intensity.
- Whether there is at least a reasonable possibility that the AE is related to the study treatment: suspected (yes) or not suspected (no). See below for further instructions on the assessment of causality.
- The start and end dates, unless unresolved at the final safety follow-up visit.
- The action taken with regard to study treatment as a result of the AE/SAE(s).
- The event outcome (eg, not recovered/not resolved, recovered/resolved, etc.).

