10.3.3. Safety Analyses

Adverse events/serious adverse events that are ongoing at the time of rollover will be regraded per CTCAE v5.0 if graded per CTCAE v4.03. Safety analyses will be conducted. Adverse events will be coded by the MedDRA dictionary, severity of AEs will be assessed using CTCAE v5.0 Grades 1 through 5, and TEAEs (ie, AEs reported for the first time in this protocol and within 30 days of last dose of study treatment, or any AE ongoing and defined as

treatment-emergent from the parent protocol) will be tabulated by preferred term and system organ class for all events, related events, and events of Grade 3 or higher. All AEs will be listed.

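### Does tying the 30-day TEAE window to when an event is reported drop events first raised at the safety follow-up visit?

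*SAP*

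**What the plan says.** SAP section 7.2.1 gives the TEAE definition two limbs. The first is "A TEAE is any AE either reported for the first time in this Protocol and within 30 days of last dose of study treatment"; the second takes in events carried over from the parent study that were already treatment-emergent there and are still ongoing. Protocol section 10.3.3 words the first limb almost identically: "AEs reported for the first time in this protocol and within 30 days of last dose of study treatment". SAP 7.2.1 then adds a default: "all AEs will be considered TEAEs unless the AE can unequivocally be defined as not treatment-emergent".

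SAP section 7.1 sets the scope of the tables: "Unless otherwise stated, table summaries will be limited to TEAEs". Listings cover all AEs whatever their timing (SAP 7.2.1).

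Protocol Table 3 schedules AE assessment on Day 1 of each cycle, at EOT and at safety follow-up. Protocol section 8.6.1 describes the follow-up visit as one "which should occur 30 to 35 days after the EOT visit", and asks of it: "Reasonable efforts should be made to have the participant return for the follow-up visit and report any AEs that may occur during this period".

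**The concern.** Most TEAE definitions attach the post-treatment window to the date an event starts. This one uses the verb for reporting, and the only scheduled contact after EOT falls at or beyond the edge of the window. If the programmer took the wording at face value, an event that started on day 12 after the last dose but was first mentioned on day 33 would not be a TEAE. A second programmer using onset would count it.

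The study has one endpoint, the frequency and nature of AEs and SAEs, and its summary tables contain only TEAEs. A rule that yields two counts from the same data would matter there, particularly with so few participants.

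**Working it through.** The plan has no figure to reproduce: there is no power calculation, and all analyses are described as exploratory (SAP 3.2, 3.3). The check has two parts.

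**1. How far the two readings could differ**

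Inputs:
- Window: 30 days after last dose (SAP 7.2.1, Protocol 10.3.3).
- Follow-up visit: d = 30 to 35 days after the EOT visit (Protocol 8.6.1).
- Lag L from last dose to the EOT visit: not given in the documents, so the values below are assumptions.
- Planned enrolment: about 20 (SAP 3.3).

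Visit day after last dose: V = L + d. A report made at the visit is inside the window only if V ≤ 30. Post-dose onset days 1 to 30 for which this visit is the only scheduled AE assessment: 30 − L.

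| L (assumed) | Visit days V | Visit days inside window | Onset days depending on the visit |
|---|---|---|---|
| 0 | 30–35 | 1 of 6 | 30 |
| 1 | 31–36 | 0 of 6 | 29 |
| 3 | 33–38 | 0 of 6 | 27 |
| 7 | 37–42 | 0 of 6 | 23 |
| 14 | 44–49 | 0 of 6 | 16 |

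Protocol section 5.1, criterion 6c, times the follow-up visit from the last dose of pemigatinib instead of from EOT. That gives days 30–35 and again 1 of 6 inside. The two sections ought to agree, but either anchor puts the visit at least 30 days after last dose, so the mismatch does not alter this question.

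For a visit on day 31 or later, an event first raised there with onset on days 1–30 is a TEAE by onset and not by report date. Events starting after day 30 are outside on both readings. One reclassified participant moves a row by 1/20 = 5 percentage points overall, or 1/10 = 10 points in a column of 10.

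**2. Which date the documents support**

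- *What is recorded.* Protocol section 9.3 lists the items evaluated for each event. The dates among them are "The start and end dates, unless unresolved at the final safety follow-up visit". No report date appears in that list.
- *What is queried.* SAP 7.2.1 requires a missing onset date to be queried. It does not mention a report date.
- *What the reporting phrase does.* It separates events new to this study from the carried-over events in the second limb. The sentence reads naturally as two conditions: new in this protocol, and falling within 30 days of last dose.
- *Neighbouring windows.* Protocol section 8.3.1 states: "Adverse events will be monitored from the time the participant signs the ICF until at least 30 days after the last dose of study treatment". Protocol section 9.4 frames the SAE window by when events occur.
- *Tie-breaker.* An event with onset inside 30 days, excluded only on a disputed reading of one verb, is not unequivocally outside. The default therefore counts it.

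All five point to onset.

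**3. Which tables could be touched**

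The events in question begin after the last dose, so they should not enter the dose reduction, interruption or discontinuation tables (3.2.18 to 3.2.20). Serious and fatal tables are largely protected by 24-hour SAE reporting. That leaves mainly tables 3.2.1, 3.2.2, 3.2.3 and 3.2.6, for non-serious events that the participant did not volunteer between visits. SAP 7.2.2 also allows a listing in place of a by-term summary when 10 or fewer participants appear in it.

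**The case for a change.** The best case for a change is that the documents can tell onset from reporting when they wish to. Protocol 8.3.1 speaks of events that begin or worsen, and Protocol 6.6 contemplates SAEs reported more than 30 days after the last dose, so late reports are foreseen. SAP 4.1.4 gives rules for the last-dose date used in the TEAE flag but never says which AE date is set against it. The default clause does not choose that date either: if report date governed, a day-33 report would be clearly outside. The 24-hour SAE clock runs from the investigator's knowledge, so an SAE first learned of at follow-up would be exposed too. Writing onset into the definition would cost one sentence and need no new data.

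The wording is indeed loose, and the visit-day counts are right. But the argument that a late report is clearly outside presupposes that report date governs, which is the point in dispute. The literal reading also requires a date that the documents do not list among the AE items.

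A fuller rewrite could do harm. Opening the window at onset on or after rollover consent could drop an event with a known earlier onset that was never recorded in the parent study; the present first limb counts it. Adding grade increases would repeat what Protocol 9.3 and SAP 7.2.1 already provide, since each change in severity is recorded as a separate AE.

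**Conclusion.** No change is needed. The definition leaves a detail unstated that analysts will fill sensibly: with start dates collected, missing onset dates queried and a default that favours counting, the TEAE flag will be built on onset. Events that began within 30 days of last dose and were first raised at follow-up will then be in the tables. Naming onset in the text would clarify the wording without altering the result.

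The potential divergence is 5 or 6 of 6 permitted visit days and about 5 percentage points per affected participant in a row based on 20. Those figures describe calendar days and the weight of one participant; they do not predict how many events are affected, which the documents cannot show. The 5-point figure shrinks slightly if more than 20 enrol.

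The conclusion assumes that the EOT visit is on or after the day of last dose and that the eCRF holds the AE dates named in Protocol 9.3. The eCRF itself was not available, so it may hold a report or entry date as well; nothing in the protocol or SAP directs its use. The analysis is descriptive, and the complete AE listing would let a reader see any event left out of a table.

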7.2.2. Adverse Event Summaries

An overall summary of AEs by dose level will include the following:

- Number (%) of participants reporting any TEAEs
- Number (%) of participants reporting any serious TEAEs
- Number (%) of participants reporting any Grade 3 or higher TEAEs
- Number (%) of participants who had any TEAEs related to pemigatinib
- Number (%) of participants who temporarily interrupted pemigatinib because of TEAEs
- Number (%) of participants who permanently discontinued from pemigatinib because of TEAEs
- Number (%) of participants who had pemigatinib dose reductions because of TEAEs
- Number (%) of participants who had any TEAEs with a fatal outcome

The following summaries will be produced by MedDRA term (if 10 or fewer participants appear in a table, a listing may be appropriate):

- Summary of TEAEs by MedDRA SOC and PT
- Summary of TEAEs by MedDRA PT in decreasing order of frequency
- Summary of Grade 3 or higher TEAEs by MedDRA SOC and PT
- Summary of serious TEAEs by MedDRA SOC and PT
- Summary of TEAEs with a fatal outcome by MedDRA SOC and PT
- Summary of pemigatinib treatment-related serious TEAEs by MedDRA SOC and PT
- Summary of TEAEs leading to pemigatinib dose reduction by MedDRA SOC and PT
- Summary of TEAEs leading to pemigatinib dose interruption by MedDRA SOC and PT
- Summary of TEAEs leading to discontinuation of pemigatinib by MedDRA SOC and PT

Listings will be provided for all AEs, SAEs, AEs of Grade 3 and higher, treatment-related AEs, fatal AEs, and AEs leading to interruption, reduction, or discontinuation of study drug. All listings will be presented for the safety population.

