3.2 Adverse Events			
3.2.1	Overall Summary of Treatment-Emergent Adverse Events	Safety	X
3.2.2	Summary of Treatment-Emergent Adverse Events by MedDRA System Organ Class and Preferred Term	Safety	X
3.2.3	Summary of Treatment-Emergent Adverse Events by MedDRA Preferred Term in Decreasing Order of Frequency	Safety	X
3.2.6	Summary of Grade 3 or Higher Treatment-Emergent Adverse Events by MedDRA System Organ Class and Preferred Term	Safety	X
3.2.8	Summary of Serious Treatment-Emergent Adverse Events by MedDRA System Organ Class and Preferred Term	Safety	X
3.2.15	Summary of Pemigatinib-Related Serious Treatment-Emergent Adverse Events by MedDRA System Organ Class and Preferred Term	Safety	X
3.2.16	Summary of Treatment-Emergent Adverse Events with a Fatal Outcome by MedDRA System Organ Class and Preferred Term	Safety	X
3.2.18	Summary of Treatment-Emergent Adverse Events Leading to Pemigatinib Dose Reduction by MedDRA System Organ Class and Preferred Term	Safety	X
3.2.19	Summary of Treatment-Emergent Adverse Events Leading to Pemigatinib Dose Interruption by MedDRA System Organ Class and Preferred Term	Safety	X
3.2.20	Summary of Treatment-Emergent Adverse Events Leading to Pemigatinib Discontinuation of Study Drug by MedDRA System Organ Class and Preferred Term	Safety	X

Listings

Listing No.	Title

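### Apart from fatal outcomes, no planned AE summary separates parent-study TEAEs still ongoing at rollover from AEs that began or worsened in this study

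*SAP*

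**What the plan says.** The definition is the same in both documents. Protocol 10.3.3 counts "AEs reported for the first time in this protocol and within 30 days of last dose of study treatment, or any AE ongoing" that was already treatment-emergent in the parent study, and SAP 7.2.1 repeats the second limb: "or any AE ongoing and defined as treatment-emergent from the parent Protocol". SAP 7.1 then sets the scope of the tables: "Unless otherwise stated, table summaries will be limited to TEAEs".

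SAP 7.2.2 plans an overall summary by dose level and a set of summaries by MedDRA term, starting with "Summary of TEAEs by MedDRA SOC and PT". Appendix A lists the matching tables, from Table 3.2.1 ("Overall Summary of Treatment-Emergent Adverse Events") onwards. All AEs are also listed.

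Data collection does make the distinction. Protocol 8.3.1 and 9.3 require AEs ongoing at rollover to be entered in this study's eCRF. A separate rule covers later events: "Adverse events for enrolled participants that begin or worsen after informed consent should be recorded on the Adverse Event Form in the eCRF". Protocol 10.3.3 adds that ongoing AEs "will be regraded per CTCAE v5.0 if graded per CTCAE v4.03". Protocol 9.3 asks for start dates and makes each change in severity its own AE record.

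**The concern.** The only objective is long-term safety and tolerability, and the only endpoint is how often AEs and SAEs occur and of what kind (SAP 2.2). No efficacy analysis is planned. Participants enter while already taking and tolerating pemigatinib (Protocol 5.1), so some may bring AEs with them.

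A count that pools those AEs with later ones describes the burden present during the study. It does not say how many participants developed something new or got worse on continued treatment. A reader of the tables could take a persistent, unchanged AE for one that arose here. The distinction is collected at the site, but no planned summary uses it.

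**Working it through.** The plan states no figure that can be reproduced, so the check is an inventory of the planned displays, followed by a bound and an illustration.

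**1. Inventory (SAP 7.2.2 and Appendix A, section 3.2)**

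| Display | Planned | Must reflect events in this study | Can mix both kinds | Restricted to or split by onset or worsening |
|---|---|---|---|---|
| Rows of the overall summary | 8 | 1 (fatal) | 7 | 0 |
| Summaries by MedDRA term | 9 | 1 (fatal) | 8 | 0 |

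One overall table plus 9 term tables gives 1 + 9 = 10, which matches the AE tables in Appendix A. The only split named is dose level.

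- *Fatal displays.* The exception is Table 3.2.16, "Summary of Treatment-Emergent Adverse Events with a Fatal Outcome by MedDRA System Organ Class and Preferred Term", with its row in the overall summary. Entrants are alive and on treatment, so a fatal outcome must occur in this study. This follows from logic and not from a stated rule.
- *Discontinuation displays.* These are not a second exception. The action falls in this study, because Protocol 5.2 excludes anyone permanently discontinued from the parent protocol. The AE behind it may still be a carried-over one that did not worsen.
- *Dose-reduction and interruption displays.* The SAP does not say that the action must occur in this study, and Protocol 2.2.2 foresees reductions made on the parent protocol.

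**2. Bound that needs no assumed rate**

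For any row, k = (participants with a new or worsened AE) + (participants with only carried-over AEs).

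- With no fatal events in the row, the first term can be anything from 0 to k. Example: 6/20 = 30% fits 0% to 30%.
- For the any-TEAE row, the lower limit is the number of participants with a fatal TEAE.
- One participant moves a column by 100/n points. With n = 20 (SAP 3.3), 100/20 = 5 points. Columns with fewer participants move by more.

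**3. Illustration on assumed inputs**

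Let p be the proportion with a new or worsened AE and q the proportion entering with an ongoing TEAE, taken as independent. The documents give neither. Then pooled = 1 − (1 − p)(1 − q), and the difference from p is q(1 − p).

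| Assumed case | p | q | Pooled | Difference |
|---|---|---|---|---|
| Any TEAE | 50% | 30% | 1 − 0.5 × 0.7 = 65% | 15 points |
| Any TEAE | 50% | 90% | 1 − 0.5 × 0.1 = 95% | 45 points |
| Any TEAE | 90% | 30% | 1 − 0.1 × 0.7 = 93% | 3 points |
| Any TEAE | 90% | 90% | 1 − 0.1 × 0.1 = 99% | 9 points |
| One PT | 10% | 10% | 1 − 0.9 × 0.9 = 19% | 9 points |
| One PT | 10% | 50% | 1 − 0.9 × 0.5 = 55% | 45 points |

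In counts: if 2 of 20 participants newly develop one PT (10%) and 1, 3 or 5 others carry it over, the table shows 3/20 = 15%, 5/20 = 25% or 7/20 = 35%.

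**4. Can the split be derived?**

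Yes. New onset follows from start dates. Worsening follows from the v5.0 grade held for ongoing AEs and the separate record for each severity change, provided that the records of one event are linked in programming.

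**The case against.** The strongest reply is that the pooling is deliberate. Protocol and SAP agree on it, treatment is uninterrupted, and rollover is an administrative date. SAP 4.1.3 declares baseline not applicable for that reason, and an AE that persists under continued dosing is itself information on long-term tolerability. All of this stands. It is why the planned tables should remain as they are and why this is not an error in the protocol-defined analysis.

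A second reply is that the listings suffice. There are about 20 participants and the analyses are exploratory. Original dates are listed, study day is negative before Day 1, and small tables may become listings. A reader could indeed separate the events by hand. But the endpoint is a frequency, and the listings provide neither a flag nor a prespecified count. A hand count would need its own decisions on regrading, on grade decreases that create new records, and on unresolved onset dates. SAP 7.2.1 has fallback rules for missing causality and severity but none for onset date.

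A third reply is that worsening is harder to derive than onset. SAP 7.2.1 grades by the worst level reached, and no identifier linking the records of one event is described. This stands as a programming task and as a reason to fix the rule in advance. It does not remove the gap.

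Finally, the 6/20 example fits a planned column only if all 20 participants are on monotherapy, since SAP 5.2 lists no grand total. That is correct; in smaller columns each participant weighs more.

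**Conclusion.** The concern holds. Outside the fatal displays, 7 overall rows and 8 summaries by MedDRA term can mix carried-over AEs with new or worsened ones, and none separates them. The tables therefore cannot show how many participants developed or worsened an AE during this study.

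How much this matters in practice is unknown, because it depends on how many participants enter with an ongoing TEAE. The bound of 0 to k rests on no assumed rate. The differences of 3 to 45 points rest on assumed rates and independence, and they are differences between two valid measures. The any-TEAE row may differ little; single-PT rows may differ more. This should be fixed, as a low-cost improvement to the reporting of the only endpoint.

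**What to change.** Leave the protocol-defined TEAE tables unchanged and add the following.

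1. **Flag (SAP 7.2.1).** Define a new-or-worsened AE, up to 30 days after last dose, as onset after signing of the rollover ICF or an increase over the CTCAE v5.0 grade at rollover. The grade at rollover is the grade after any regrading; regrading itself and grade decreases do not count as worsening. Link the records of one event so that a decrease is not taken as a new onset. State that the anchor is consent, as in the Protocol's recording rule, whereas SAP study day counts from first dose.
2. **Unclear onset dates.** An AE recorded as ongoing at rollover is carried over whatever its partial onset date; the parent-study ID link (Protocol 8.1.2) allows a check. Any other AE with an unresolved onset date counts as new unless the known part places it before consent.
3. **Displays (SAP 7.2.2 and Appendix A).** Add rows for flagged AEs to Table 3.2.1 and one SOC/PT table of flagged AEs, with Grade 3 or higher and serious events shown, or listed where few. Show the flag in the AE listings.
4. **Clarification only.** State that the dose-reduction and dose-interruption summaries count actions taken in this study.

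The cost is one derived variable, a few rows, one table, a listing column and the programming to link records. The new displays will have smaller, less precise counts. SAP 7.2.1 needs a short addition; Appendix A allows its lists to change without an amendment where the nature of the analysis is unaffected. No new data or participants are needed.
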